8.1.2. Definition of Serious Adverse Event

If an event is not an AE per Section 8.1.1, then it cannot be an SAE even if serious conditions are met (e.g., hospitalization for signs/symptoms of the disease under study, death due to progression of disease, etc.).

An SAE is any untoward medical occurrence that, at any dose:

- Results in death
- Is life-threatening
 - The term “life-threatening” refers to an event in which the subject was at risk of death at the time of the event; does not refer to an event, which hypothetically might have caused death, if it were more severe.
- Requires hospitalization or prolongation of existing hospitalization
 - In general, this signifies that the subject has been detained (usually involving at least an overnight stay) at the hospital or emergency ward for observation and/or treatment that would not have been appropriate in the physician's office or out-patient setting. Complications that occur during hospitalization are AEs. If a complication prolongs hospitalization or fulfills any other serious criteria, the event is serious. When in doubt as to whether “hospitalization” occurred or was necessary, the AE should be considered serious. Hospitalization for elective treatment of a pre-existing condition that did not worsen from baseline is not considered an AE.
- Results in disability/incapacity: a substantial disruption of a person's ability to conduct normal life functions
 - This definition is not intended to include experiences of relatively minor medical significance such as uncomplicated headache, nausea, vomiting, diarrhea,

influenza, and accidental trauma (e.g., sprained ankle), which may interfere or prevent everyday life functions but do not constitute a substantial disruption.

- Results in a congenital anomaly/birth defect
- Medical or scientific judgment should be exercised in deciding whether reporting is appropriate in other situations, such as important medical events that may not be immediately life-threatening or result in death or hospitalization but may jeopardize the subject or may require medical or surgical intervention to prevent one of the other outcomes listed in the above definition. These should also be considered serious. Examples of such events are invasive or malignant cancers, intensive treatment in an emergency room or at home for allergic bronchospasm, blood dyscrasias, or convulsions that do not result in hospitalization, or development of drug dependency or drug abuse.

8.1.3. Adverse Events of Special Interest

In prior clinical studies, the following AEs have been identified as AEs of particular clinical importance and will be reported as AESIs in this study; in each case, study drug may be discontinued, and study drug may be restarted when event resolves:

- Contact dermatitis: the study site should collect location, duration, size, associated symptoms (itching, burning, pain), severity (mild, moderate, severe), and photograph the affected site (if possible). If the subject contacts the study site to report significant skin irritation at or near the site of study drug application between study visits, the subject should be brought for an unscheduled visit, if possible.
- Folliculitis: the study site should collect the location, duration, size, associated symptoms (itching, burning, pain), severity (mild, moderate, severe), indicate whether pustular, and photograph the affected site (if possible)
- Headache: the study site should collect duration, severity (mild, moderate, severe), onset, and location

Additional AESIs may be identified by the Drug Safety Physician and if applicable by the Clinical Study Team Physician during the evaluation of safety data for the Clinical Study Report. For each AESI, a narrative may be written and included in the Clinical Study Report.

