4.6.1. Reasons for Withdrawal from Study

Study drug will be discontinued for any of the following reasons:

- Subject has an AE that is considered to be related to study drug or procedures AND is severe enough to warrant treatment discontinuation, as determined by the Investigator (Section 8.1)
- Subject requires concurrent prohibited concomitant medication during the study. If, in the opinion of the Investigator and the study Medical Monitor, such medication will not interfere with the conduct or interpretation of the study or compromise the safety of the subject, then the subject may continue to receive study drug. If the subject is discontinued from study drug, they may remain in the study for safety assessments as needed, at the discretion of the Investigator and Medical Monitor.
- Pregnancy
- Any Grade 3 or 4 AE considered causally related to study drug (Section 8.2.2)

Study drug may be discontinued for any of the following reasons:

- Subject noncompliance
- Investigator noncompliance
- Discontinuation of the study at the request of the Sponsor, regulatory agency, or an Institutional Review Board (IRB)/Independent Ethics Committee (IEC)

If a subject meets a withdrawal criterion during treatment, an Early Termination Visit will be required (Section 7.7).

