8.2. Classification of Adverse Events

8.2.1. Assigning Severity Rating for Adverse Events

8.2.1.1. Criteria for Determining Adverse Event Severity

The Investigator will make an assessment of the severity of each AE and SAE according to the National Cancer Institute Common Terminology Criteria for Adverse Events (CTCAE), v. 5.0, 2017. For terms not specified with the CTCAE, the criteria in [Table 4](#) should be used to determine the grade severity.

Table 4: Criteria for Determining the Grade/Severity of Adverse Event Terms Not Specified by the National Cancer Institute CTCAE

Grade	Criteria
1	Mild; asymptomatic or mild symptoms, clinical or diagnostic observations only; intervention not indicated
2	Moderate; minimal, local, or noninvasive intervention indicated; limiting age-appropriate instrumental activities of daily living ^a
3	Severe or medically significant but not immediately life-threatening; hospitalization or prolongation of hospitalization indicated; disabling; limiting self-care activities of daily living ^b
4	Life threatening consequences; urgent intervention indicated
5	Death related to adverse event

CTCAE = Common Terminology Criteria for Adverse Events.

^a Instrumental activities of daily living refer to preparing meals, shopping for groceries or clothes, using the telephone, managing money, etc.

^b Self-care activities of daily living refer to bathing, dressing and undressing, feeding self, using the toilet, taking medications, and not bedridden.

Adverse event severity should be recorded in the appropriate section of the adverse event case report form and in the subject's source documents.

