8.2.1.2.2. Grade 3 Adverse Event

Subjects who develop a Grade 3 AE should be managed as follows:

- If the Investigator has compelling evidence that the Grade 3 AE has not been caused by study drug, then dosing may continue after discussion with the Medical Monitor.
- Subjects who develop a Grade 3 AE that the Investigator considers related or possibly related to study drug should have the study drug discontinued. Subjects experiencing Grade 3 AEs requiring permanent discontinuation of study drug should be followed weekly until resolution or stability of the AE and encouraged to have withdrawal study evaluations completed.

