8.2.1.2.3. Grade 4 Adverse Event

Subjects who develop a Grade 4 AE should have study drug permanently discontinued.

Subjects experiencing Grade 4 AEs requiring permanent discontinuation of study drug should be followed weekly until resolution or stability of the AE and encouraged to have withdrawal study evaluations completed.

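### Protocol 8.1.3 lets study drug be restarted after any adverse event of special interest without limit, against the stops in 4.6.1 and 8.2.1.2.3 and the interruption rule in 4.6.2 (minor; patient safety)

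*Protocol*

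**What the plan says.** Protocol 8.1.3 names three adverse events of special interest (AESIs): contact dermatitis, folliculitis and headache. One drug-handling rule covers all three: "in each case, study drug may be discontinued, and study drug may be restarted when event resolves". Severe events fall within it, because the site records a severity of mild, moderate or severe for each type; the headache entry, for example, reads "Headache: the study site should collect duration, severity (mild, moderate, severe), onset, and location".

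Four other places deal with stopping drug:

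- **4.6.1** lists reasons for which drug *will* be stopped, including "Any Grade 3 or 4 AE considered causally related to study drug". It adds: "If a subject meets a withdrawal criterion during treatment, an Early Termination Visit will be required". It gives no route back to treatment.
- **8.2.1.2.2** (Grade 3): "If the Investigator has compelling evidence that the Grade 3 AE has not been caused by study drug, then dosing may continue". The Medical Monitor has to be consulted first. Otherwise, subjects whose event the Investigator considers "related or possibly related to study drug should have the study drug discontinued".
- **8.2.1.2.3**: "Subjects who develop a Grade 4 AE should have study drug permanently discontinued", with no causality condition.
- **4.6.2** says that, while an episode of worsening or a PGA of 2 or more is being treated, the study makes no provision for temporary interruption except for skin irritation. The Medical Monitor is contacted about any safety interruption.

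None of these sections exempts AESIs, 8.1.3 refers to none of them, and no order of precedence is stated.

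**The concern.** Both halves of the 8.1.3 rule cause difficulty. The first makes stopping optional where 4.6.1 makes it compulsory. The second permits a restart where 4.6.1 ends treatment with a termination visit and where 8.2.1.2.3 calls for a permanent stop. Because 8.1.3 is the text written specifically for AESIs and applies to each of them, a site could take it as an exception to the general rules.

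What is at stake is mainly safety: re-exposure after a related Grade 3 reaction, or after any Grade 4 reaction, in a subject whom other sections take off drug. These are not obscure terms. Protocol 1.3.1.1 and 1.3.1.2 report folliculitis and contact dermatitis as the most frequent dermatologic events in the psoriasis dose-ranging study, and headache as one of the two most frequent nondermatological events there. With about 100 to 120 sites (4.1) and no independent Data Monitoring Committee (8.6), the re-exposure rule should not have to be inferred.

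A lesser consequence is uneven handling. SAP 11.1 tabulates permanent withdrawals and interruptions due to adverse events, so the same event could end as an interruption at one site and a withdrawal at another.

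**Working it through.** No arithmetic applies. The check is to take each grade and causality in turn and ask whether a site can follow 8.1.3 as written and also follow the other sections.

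| AESI | Other sections | 8.1.3 | Result |
|---|---|---|---|
| Grade 1 or 2 | 8.2.1.2.1: continue at Investigator's discretion | Stop optional, restart allowed | No conflict with the grade rules |
| Grade 3, compelling evidence against causation | 8.2.1.2.2: dosing may continue after Medical Monitor discussion | Same | No conflict |
| Grade 3, related | 4.6.1: compulsory stop and Early Termination Visit. 8.2.1.2.2: should stop | Same | Conflict with 4.6.1 on stop and restart; with 8.2.1.2.2 on the stop |
| Grade 3, possibly related | 8.2.1.2.2: should stop | Same | Conflict on the stop only |
| Grade 4, any causality | 8.2.1.2.3: permanent stop. 4.6.1 also applies if related | Same | Conflict on stop and restart |
| Headache, any grade, during a course for PGA of 2 or more | 4.6.2: interruption recognised only for skin irritation | Same | Conflict on whether a temporary stop exists |

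Three details decide how far the table can be pressed.

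1. *Do AESIs reach Grade 3?* Under 8.2.1.1 every adverse event is graded by CTCAE, and SAP 11.11.1 summarises AESIs by grade. For terms that CTCAE does not specify, Table 4 describes Grade 3 as "Severe or medically significant but not immediately life-threatening". Whether that table or CTCAE's own entry applies to these three terms cannot be settled from the documents. Either way, 8.1.3 covers events recorded as severe and sets no upper grade.

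2. *How firm is each stop rule?* Section 4.6.1 uses *will* and treats the event as a withdrawal criterion. Sections 8.2.1.2.2 and 8.2.1.2.3 use *should*. Section 8.2.1.2.3 says the stop is permanent. The stop instruction in 8.2.1.2.2 does not, and the next sentence refers separately to Grade 3 events that need permanent discontinuation. The firm conflicts over restart are therefore with 4.6.1 and 8.2.1.2.3.

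3. *Which AESIs does 4.6.2 leave out?* Contact dermatitis fits within skin irritation and folliculitis arguably does. Headache does not, so 8.1.3 creates a stop-and-restart route that 4.6.2 says is absent.

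**The case against.** The strongest reply is that 8.1.3 only grants permission while 4.6.1 imposes a duty. A site can satisfy both by using the permission only where no compulsory stop applies. Section 8.1.3 sits among definitions and reporting, whereas drug handling by grade has its own section covering every adverse event. There are safeguards too: the Medical Monitor is contacted about any safety interruption (4.6.2) and notified of severe signs or symptoms that put the subject at risk (8.2.1.2.4). The AESI severity field also has no life-threatening level, which makes the Grade 4 branch largely theoretical for these events.

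Much of this stands. It is the likely intent, and it keeps the point minor. It does not remove the conflict, because nothing in the documents says that the permission operates inside the other rules. Nor does it address headache under 4.6.2.

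A reader might infer three stronger things that the documents do not support:

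- **That an AESI exception was intended.** Appendix 6 records that the wording in 8.1.3 on stopping was changed from compulsory to optional. That fits an exception, but it fits equally well with aligning 8.1.3 to the discretion for Grade 1 and 2 events in 8.2.1.2.1.
- **That 8.2.1.2.2 bars every restart after a related Grade 3 event.** As shown above, its wording leaves room for stops that are not permanent. The bar comes from 4.6.1.
- **That results or exposure counts are materially affected.** An individual subject's exposure would differ between the two routes, but the documents do not allow the number of such subjects to be derived. The SAP 11.1 tables would record what each site did, so they would not be misclassified.

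**Conclusion.** Wrong as written, and minor. Section 8.1.3 permits an optional stop and a restart for every AESI, which conflicts with 4.6.1 for related Grade 3 or 4 events, with 8.2.1.2.3 for any Grade 4 event, and with 4.6.2 for headache during a treatment course. The stricter sections probably govern, but 8.1.3 does not say so.

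The size cannot be put as a number. Few subjects are likely to be involved: Protocol 1.1.1 describes most treatment-emergent events in the Phase 2b studies as mild or moderate. SAP 10.1 makes all summaries descriptive with no testing, so no inferential result depends on this. The conclusion rests on the current text alone and assumes only that at least some AESIs can be graded 3 or higher.

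**What to change.** Two wording changes:

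1. **8.1.3**, in place of the present rule on stopping and restarting: *Subject to Sections 4.6.1 and 8.2.1.2, study drug may be interrupted for an AESI and restarted when the event resolves, with the Medical Monitor contacted (Section 4.6.2); study drug is not restarted after a Grade 3 AESI considered causally related to study drug or after any Grade 4 AESI.*
2. **4.6.2**: extend the exception to *skin irritation or an AESI (Section 8.1.3)*.

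Leave 8.2.1.2.2 as it stands. Section 8.2.2 offers only two causality categories, so it may be tempting to delete the possibly-related wording there. That would narrow a safety stop, because an event judged only possibly related would lose its instruction to stop. Making every Grade 3 stop in that section permanent would be a policy change and not a clarification.

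The cost is wording only: no new assessment, no new data collection and no SAP change. Under 11.2.1 the change goes to the IRB or IEC and to regulatory authorities and needs approval before use, so it is best bundled with the next amendment.

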8.2. Classification of Adverse Events

8.2.1. Assigning Severity Rating for Adverse Events

8.2.1.1. Criteria for Determining Adverse Event Severity

The Investigator will make an assessment of the severity of each AE and SAE according to the National Cancer Institute Common Terminology Criteria for Adverse Events (CTCAE), v. 5.0, 2017. For terms not specified with the CTCAE, the criteria in [Table 4](#) should be used to determine the grade severity.

Table 4: Criteria for Determining the Grade/Severity of Adverse Event Terms Not Specified by the National Cancer Institute CTCAE

Grade	Criteria
1	Mild; asymptomatic or mild symptoms, clinical or diagnostic observations only; intervention not indicated
2	Moderate; minimal, local, or noninvasive intervention indicated; limiting age-appropriate instrumental activities of daily living ^a
3	Severe or medically significant but not immediately life-threatening; hospitalization or prolongation of hospitalization indicated; disabling; limiting self-care activities of daily living ^b
4	Life threatening consequences; urgent intervention indicated
5	Death related to adverse event

CTCAE = Common Terminology Criteria for Adverse Events.

^a Instrumental activities of daily living refer to preparing meals, shopping for groceries or clothes, using the telephone, managing money, etc.

^b Self-care activities of daily living refer to bathing, dressing and undressing, feeding self, using the toilet, taking medications, and not bedridden.

Adverse event severity should be recorded in the appropriate section of the adverse event case report form and in the subject's source documents.

8.2.1.2. Toxicity Management Criteria

8.2.1.2.1. Grade 1 or Grade 2 Adverse Event

Subjects who develop a Grade 1 or Grade 2 AE may continue study drug at the discretion of the Investigator. Subjects who choose to withdraw from study due to a Grade 1 or 2 AE should have study withdrawal / follow-up evaluations completed.

8.2.1.2.2. Grade 3 Adverse Event

Subjects who develop a Grade 3 AE should be managed as follows:

- If the Investigator has compelling evidence that the Grade 3 AE has not been caused by study drug, then dosing may continue after discussion with the Medical Monitor.
- Subjects who develop a Grade 3 AE that the Investigator considers related or possibly related to study drug should have the study drug discontinued. Subjects experiencing Grade 3 AEs requiring permanent discontinuation of study drug should be followed weekly until resolution or stability of the AE and encouraged to have withdrawal study evaluations completed.

8.2.1.2.3. Grade 4 Adverse Event

Subjects who develop a Grade 4 AE should have study drug permanently discontinued.

Subjects experiencing Grade 4 AEs requiring permanent discontinuation of study drug should be followed weekly until resolution or stability of the AE and encouraged to have withdrawal study evaluations completed.

8.2.1.2.4. Other Management Criteria

The Medical Monitor should be notified if any of the following occur:

- Severe signs or symptoms, or significant changes in any of the safety assessments, that put the safety of the subject at risk (e.g., laboratory tests or vital signs, etc.) as judged by the Investigator

8.2.2. Assigning Causal Relationship to Study Drug

An Investigator is to make the causality assessment. Causality assessment may only be delegated to a Principal Investigator or Sub-Investigator; however, if it is delegated to any other staff, this must be recorded as a protocol deviation. The reasonable possibility of the relationship of an adverse event to study drug is to be assessed with careful medical consideration at the time of evaluation of an adverse event. The following definitions are to be used for the relationship of the adverse event to study drug:

- **Related:** A clinical event, including laboratory test abnormality, with a temporal relationship to study drug administration that makes a causal relationship plausible, unlikely attributed to concurrent disease or other drugs or chemicals, and that follows a clinically reasonable response on readministration (rechallenge) with or withdrawal (dechallenge) from study drug, although information on drug withdrawal may be lacking or unclear
- **Not related:** A clinical event, including laboratory test abnormality, with a temporal relationship to study drug administration that makes a causal relationship improbable and/or in which other drugs, chemicals, or underlying disease provide a plausible explanation

Any AEs/SAEs assessed as related to study participation (e.g., protocol-mandated procedures, invasive tests, or change in existing therapy) or related to study drug will be collected from the time a subject consents to participate in the study up to and including any follow-up contact.

All AEs, whether related to study drug or not, must be fully and completely documented on the AE page of the eCRF and in the subject's clinical record. In the event a subject is withdrawn from the study because of an adverse event, the primary reason for withdrawal (e.g., due to an adverse event) must be recorded on the eCRF as such.

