10.4.3. Safety Analyses

The number and percent of subjects with TEAEs will be summarized by system organ class and preferred term for all TEAEs, all TEAEs considered by the Investigator to be related to study drug, all SAEs, and all TEAEs leading to study drug discontinuation. All adverse event summaries will include information for adverse events that occurred after administration of the first dose of study drug until completion of the final study visit. Data listings will be provided for subjects who discontinued the study due to an adverse event and for subjects with an SAE.

Selected clinical laboratory data will be analyzed using descriptive summary statistics, including the number of nonmissing observations, mean and SD, median, upper and lower quartiles, minimum and maximum for values and changes from Baseline. Categorical safety data will be analyzed using frequency tables and, if applicable, shift tables.

Vital signs will be listed by subject and summarized by visit.

Mean scores from the LTS will be summarized by visit.

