11.11.1 Adverse Events

AE terms will be coded using Medical Dictionary for Regulatory Activities (MedDRA) dictionary. All AEs reported in current study are considered as treatment-emergent AE (TEAE) except for those AEs ongoing at the end of pivotal studies but resolved prior to the Visit 1 date in the extension study.

All TEAEs will be listed by subject, detailing the verbatim term given by the investigator, the preferred term (PT), system organ class (SOC), onset date and time, end date and time, ongoing at the end of pivotal studies (Y/N), duration (days), CTCAE grade, outcome, relationship to study drug, action taken with study drug, other action taken to treat the event, AE of special interest (Y/N), seriousness and criteria for seriousness.

AEs resolved prior to the Visit 1 date, Serious TEAEs (STEAEs), TEAEs leading to study discontinuation and TEAEs related to study drug will also be listed separately. The following adverse events of special interest (AESIs) will be identified and listed separately: contact dermatitis, folliculitis, and headache.

The number and percent of subjects with TEAEs will be summarized as incidence rates of:

- Any TEAE
- Any TEAE Excluding Those Ongoing at the end of the Pivotal Studies
- Any TEAE Ongoing at the end of the Pivotal Studies
- Any treatment-emergent AESIs
- Any treatment-emergent AESIs Excluding Those Ongoing at the end of the Pivotal Studies
- Any treatment-emergent AESIs Ongoing at the end of the Pivotal Studies
- Any treatment-related TEAE
- Any TEAE leading to study drug discontinuation
- Any TEAE leading to study discontinuation
- Any serious TEAE

- Death
- Treatment-related Serious TEAE
- Serious TEAE leading to study drug discontinuation
- Serious TEAE leading to study discontinuation
- TEAE (COVID-19)

Individual PTs will be summarized by SOC in alphabetical order and PT in descending order of frequency for the following subsets and subgroupings:

- All TEAEs
- All TEAEs by maximum CTCAE grade
- All TEAEs by maximum causality (not related, related) to the study drug
- All TEAEs Excluding Those Ongoing at the End of the Pivotal Studies
- All TEAEs ongoing at the end of the pivotal studies
- All treatment-related TEAEs
- All TEAEs leading to study discontinuation
- All TEAEs leading to study drug discontinuation
- All serious TEAEs

All TEAEs and all serious TEAEs will also be summarized by SOC (alphabetical order) and PT (descending order) for the following subgroups:

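### Protocol 8.2.2 asks for a reasonable-possibility judgement, but its two categories class an event with both a plausible drug cause and a plausible other cause as Not related, so the causality-based safety tables may read low

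*Protocol*

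**What the plan says.** Protocol 8.2.2 opens with the standard: "The reasonable possibility of the relationship of an adverse event to study drug is to be assessed with careful medical consideration". It then gives the definitions to be used, of which there are two.

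- *Related* needs timing that makes a drug cause plausible, and the event must be "unlikely attributed to concurrent disease or other drugs or chemicals". It also refers to the response on withdrawal or re-exposure, but allows withdrawal information to be missing.
- *Not related* has two limbs. The first is an event "with a temporal relationship to study drug administration that makes a causal relationship improbable". The second limb, which can apply together with the first or on its own, reads: "and/or in which other drugs, chemicals, or underlying disease provide a plausible explanation".

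Protocol 10.4.3 summarises "all TEAEs considered by the Investigator to be related to study drug". SAP 11.11.1 keeps the two-level scale ("All TEAEs by maximum causality (not related, related) to the study drug") and adds treatment-related and treatment-related serious TEAE summaries, as well as causality within the AESI summaries. SAP section 8 counts an event with missing causality as related.

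Other sections use other causality terms. Protocol 4.6.1 speaks of Grade 3 or 4 events considered causally related. Protocol 8.2.1.2.2 adds a possibly-related class for Grade 3 events.

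On contact dermatitis, folliculitis and headache, Protocol 8.1.3 says: "In prior clinical studies, the following AEs have been identified as AEs of particular clinical importance".

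**The concern.** The stated standard and the definitions give different answers for the same event. Under a reasonable-possibility standard, a plausible alternative does not by itself rule the drug out. Under the *Not related* definition it does, because the joining words make either limb sufficient.

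Safety is the first objective of this study, which is open-label with no concurrent control arm, and interim results are to be presented when the marketing application is prepared. The treatment-related tables will be read as the investigators' view of what the drug caused. If sites follow the definitions as written, those tables rest on a narrower notion of relatedness than the one the protocol announces, and nothing in the planned outputs tells the reader so. The same judgement also feeds the discontinuation text in 4.6.1 and 8.2.1.2.2, where the terms do not match.

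**Working it through.** There is no plan figure to reproduce, so the check is mainly textual.

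**Step 1: apply both definitions to the four possible cases.**

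| Timing makes drug cause plausible | Plausible other cause | *Related* met | *Not related* met |
|---|---|---|---|
| Yes | No (other cause unlikely) | Yes | No |
| Yes | Yes | No: other cause is not unlikely | Yes: second limb alone |
| No | Yes | No | Yes: both limbs |
| No | No | No | Yes: first limb |

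Only the second row is in dispute. A reasonable possibility of a drug cause exists there, yet the definitions put the event in *Not related*. The withdrawal and re-exposure element of *Related* can only make that category narrower, so it does not change this row.

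**Step 2: look for a rule that corrects it.** The SAP imputes only missing causality. A recorded *Not related* stands. No intermediate category exists in 8.2.2 or in the SAP.

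**Step 3: separate the outputs.**

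- Dependent on the investigator's call: treatment-related TEAEs, treatment-related serious TEAEs, TEAEs by maximum causality, and the causality rows of the AESI summaries.
- Not dependent on it: all TEAEs, all serious TEAEs, TEAEs by grade and by onset period, AESI incidence, listings and summaries by type, and the Kaplan-Meier figure for each AESI.

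**Step 4: compare the causality terms.** A Grade 3 event in the disputed row is *Not related* under 8.2.2, so on that reading it does not trigger the 4.6.1 criterion. Under 8.2.1.2.2 it might count as possibly related, a term that 8.2.2 does not define. That section also asks for compelling evidence of no drug cause before dosing may continue. The three passages cannot be applied together as they stand.

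**Step 5: illustrate direction only.** Let N be planned enrolment (850, Protocol 10.2). Let r be an assumed share of subjects with a truly drug-related event (10%). Let f be the assumed share of those subjects in whom every such event also has a plausible other cause. Neither r nor f is in the documents.

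Subjects shown as related = N × r × (1 − f), and N × r = 850 × 0.10 = 85.

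- f = 25%: 85 × 0.75 = 63.75, about 64 (7.5%)
- f = 50%: 85 × 0.50 = 42.5, about 43 (5.0%)
- f = 75%: 85 × 0.25 = 21.25, about 21 (2.5%)

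The all-causality tables include all 85 at every f.

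The tables count subjects, each classified by the closest relationship (SAP 11.11.1), so a share q of *events* is not the same as f. With k independent drug-related events per subject, f = q^k. For q = 50% and k = 2, f = 0.5 × 0.5 = 25%, so the subject-level loss is a quarter rather than a half.

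**The case against.** The strongest reply is that 8.2.2 calls for careful medical judgement. Whether an alternative really explains an event is part of that judgement, so investigators may in practice apply the reasonable-possibility standard. This stands as a limit on what can be claimed about the size of the effect. It does not remove the conflict, because the definitions are stated as the ones to be used.

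A reader might infer that drug-caused contact dermatitis, folliculitis and headache would drop out of the safety report. The documents do not support that. These three are AESIs, listed and summarised by type whatever their causality, and they are the best-protected events in the plan. How often they have another plausible cause is clinical opinion that the documents do not supply.

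A reader might also infer that a merely plausible alternative lets a subject stay on drug after a Grade 3 event. Protocol 8.2.1.2.2 points the other way, since it requires compelling evidence and a discussion with the Medical Monitor. Grade 4 events under 8.2.1.2.3 and SAE reporting under 8.4.1 do not depend on causality at all.

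Nor is investigator causality the only information on attribution. Application-site location, local tolerability scores, onset-period tables and the on/off treatment cycles all help. Finally, missing causality counted as related, and background events called related, push upward, so the net error against the truth is not known. These points stand. What remains is a bias in one identified class of events, measured against the protocol's own standard.

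**Conclusion.** The inconsistency is real and can be verified within 8.2.2 alone. Followed as written, the definitions place every could-be-either event in *Not related*, so the causality-based outputs may be biased downward relative to the standard the protocol states. The documents do not allow the amount to be estimated, and the figures in the working rest on assumed values and literal application of the wording.

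The effect is confined to the causality-based outputs. The all-causality TEAE and AESI results are untouched, and no test or power calculation depends on the point because the study is descriptive. The mismatch with the causality terms in 4.6.1 and 8.2.1.2.2 is a separate textual conflict that needs to be resolved with it.

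**What to change.** Reword the two categories in 8.2.2 so that they are complementary, share one boundary, and agree with the reasonable-possibility standard stated there. Say explicitly where an event with both a plausible drug cause and a plausible other cause belongs.

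In the same amendment, reconcile the causality terms in 4.6.1, 8.2.1.2.2 and 8.2.2, and either define the possibly-related class or stop using it. Because 8.2.2 feeds the discontinuation text, the sponsor's clinical team must decide how those passages should read together. This point takes no view on which discontinuation rule is right.

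For events already assessed, do not recode. State the definition used in a footnote to the treatment-related tables. If new wording takes effect during the study, the footnote should also say that two definitions are mixed. No extra AESI output is needed, since the all-causality figures are already planned.

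The cost is a short protocol wording change, a note to sites and a table footnote. The downside is that the related-AE rate may look less favourable, and may be less comparable with the pivotal studies if they used the same wording.
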